Gender differences have been observed in the incidence, development and progression of Alzheimer's disease, and in response to interventions targeting cognitive impairment. Women develop cognitive disability more rapidly compared to men.^{13,14} Previous studies of intranasal insulin for cognition showed functional abilities were better preserved in women compared to men.¹⁵ These differences highlight the importance of evaluating responses to any agent in both males and females. As part of this proposed project we will evaluate potential gender differences in bioavailability and pharmacokinetics.

C.2. *Centella asiatica*

Centella asiatica is a highly regarded botanical reputed in Eastern medicine to increase intelligence and memory.¹⁶ In Western countries, it is sold as the dietary supplement "gotu kola"¹⁷ for use in improving brain health and cognitive function. Preclinical studies have shown that *Centella asiatica* extracts have biological effects of relevance to memory, learning, aging, mood and potentially disease progression in Alzheimer's disease.¹⁸ Water extracts of *Centella asiatica* have improved learning and memory in wild-type rats,¹⁹ wild-type mice,^{20,21} and rats subjected to central nervous system toxicity.^{22,23} In addition, similar extracts have been shown to modify the brain structure by increasing hippocampal neuron dendritic arborization in adult rats,²⁴ neonatal rats,²⁵ and neonatal mice,²¹ potentially contributing to the observed cognitive changes. With regards to mood and behavior, ethanol extracts given to mice subjected to chronic and acute stress²⁶ and sleep deprivation²⁷ demonstrated anxiolytic properties. Similar ethanol extracts revealed antidepressant properties in rats.²⁸

Figure 1. *Centella asiatica* water extract improves learning and memory in aged female Tg2576 mice without altering β -amyloid accumulation. Tg2576 mice (20 month old) were exposed to *Centella asiatica* water extract (200mg/kg/day) in their drinking water for 2 weeks before and during testing (total 5 weeks). Left – Morris water maze escape times. Right – Soluble and insoluble fractions of A β were extracted from cortical tissue and analyzed via ELISA (bars represent means +/- standard error).

[figure not shown]
Study Title: A pharmacokinetic study of *Centella asiatica* in the elderly

Principal Investigator: [name]

IRB#: 17697

Date: Feb 28 2024

Protocol v4.0

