Study Title: A pharmacokinetic study of *Centella asiatica* in the elderly

Principal Investigator: [name]

IRB#: 17697

Date: Feb 28 2024

Protocol v4.0

[figure not shown]
[figure not shown]
[figure not shown]
[figure not shown]

Figure 2. Pharmacokinetic profile of monocaffeoylquinic acids, dicaffeoylquinic acids and metabolites caffeic acid and ferulic acid in wild-type female mice. Six-month-old female mice (n=39) were administered *Centella asiatica* water extract (200 mg/kg) via oral gavage. Four mice were euthanized per time point and blood collected via cardiac puncture for analysis with HPLC-MS/MS.

F. RESEARCH DESIGN AND METHODS

F.1. Study design

This is a phase 1 pilot clinical study using a blinded randomized crossover design.

Randomization will use an arm equivalence design to promote equal numbers of participants for each order schema. We will dispense a single administration of a *Centella asiatica* water extract

Study Title: A pharmacokinetic study of *Centella asiatica* in the elderly

Principal Investigator: [name]

IRB#: 17697

Date: Feb 28 2024

Protocol v4.0

product to the research participants at two doses (2g and 4g) on two separate occasions two to four weeks apart (Figure 3). Participants will be required to adhere to a “low phytochemical diet” known as a “low plant diet” designed by the Oregon Clinical and Translational Research Institute’s (OCTRI) Bionutrition Department for 48 hours immediately preceding each study visit and for the duration of each study visit (Section I.4.). We will provide participants a handout at screening outlining the diet with meal examples. Serial blood samples (2 teaspoons; 10 mL/sample) will be obtained through a peripheral intravenous catheter, once prior to *Centella asiatica* consumption and then over a 12-hour post-administration period (15, 30, 45, 60, 90, 120, 180, 240, 360, 480, 600, and 720 min). Participants will also perform a 12-hour urine collection at each study visit to assess for excretion of *Centella asiatica* metabolites. Adverse events and tolerability will be assessed with questionnaires in-person at each study visit, by phone 24 hours after each study visit, and one week following study completion (Figure 3).

F.2. Study Population

F.2.1. Number of participants

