Eight non-demented elderly volunteers (n=4 each female and male) 65-85 years of age will be screened and enrolled in the study. We estimate that we will need to screen approximately twelve potential participants to meet the eight volunteers needed to complete the study. We expect a 10% drop out rate. We are still powered to see changes from baseline and differences between doses with a 25% drop out rate resulting in 6 subjects.

F.2.2. Inclusion and exclusion criteria

Inclusion criteria:

1. Age 65-85, male and female
2. Sufficient English language skills to complete all tests
3. Sufficient vision and hearing to complete all tests
4. No known allergies to *Centella asiatica*, (**excipients redacted**) or any of their derivatives
5. Willingness to discontinue all botanical dietary supplements for one week prior to and during each study visit
6. Willingness to comply with a 48-hour low plant diet for each study visit
7. Absence of significant depression symptoms (Geriatric Depression Scale-15 score of <12)
8. Body Mass Index (BMI) greater than 17 and less than 35 at screening
9. Non-demented, defined as Clinical Dementia Rating (CDR) score of zero and Mini Mental State Examination (MMSE) score >28
10. General health status that will not interfere with the ability to complete the study

Exclusion criteria:

1. Current smoking, alcohol or substance abuse according to DSM-V criteria
2. Women who are pregnant, planning to become pregnant or breastfeeding
3. Men who are actively trying to conceive a child or planning to within three months of study completion
4. Severe aversion to venipuncture
5. Abnormal laboratory evaluation indicating asymptomatic and untreated urinary tract infection
6. Cancer within the last five years, with the exception of localized prostate cancer (Gleason Grade <3) and non-metastatic skin cancers
7. Comorbid conditions such as diabetes mellitus, kidney failure, liver failure, hepatitis, blood disorders, clinical symptomatic orthostatic hypotension, and unstable or

Study Title: A pharmacokinetic study of *Centella asiatica* in the elderly

Principal Investigator: [name]

IRB#: 17697

Date: Feb 28 2024

Protocol v4.0

- significantly symptomatic cardiovascular disease
- 8. Significant disease of the central nervous system such as brain tumor, seizure disorder, subdural hematoma, cranial arteritis, or clinically significant stroke
- 9. Major depression, schizophrenia, or other major psychiatric disorder defined by DSM-V criteria

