Study Title: A pharmacokinetic study of *Centella asiatica* in the elderly

Principal Investigator: [name]

IRB#: 17697

Date: Feb 28 2024

Protocol v4.0

G. RECRUITMENT

Participants will be enrolled on a rolling basis until the desired number of participants is achieved. We will recruit from the Oregon Clinical and Translational Research Institute's volunteer repository, with over 40 qualifying participants identified with preliminary searches, the National Institute of Neurological Disorders and Stroke (NINDS) NeuroNext database, and the Oregon Alzheimer Disease Center's participant database. Potential participants available through the above databases will be mailed a study advertisement describing the study and requesting they call if they are interested in participation. The study will be advertised using fliers in OHSU clinics and local retirement communities/elder care facilities and an online posting in the March Wellness "March Stride" e-mail newsletter. In addition, it will be advertised using the NIH Clinical Trials website, local newspapers and radio announcements. It will be emphasized that participation in the study is completely voluntary. Copies of all advertisements have been submitted with this application for IRB approval .

G.1. Incentives

Participants will be given the option of complimentary transportation by taxi to and from their study visits (up to \$50 per visit) or a parking permit for each study visit. They will not be provided with transportation for screening visits. To compensate them for their time and effort, participants will receive \$80 for completion of the study via the ClinCard. Prorated amounts of \$40 per study visit will be implemented for participants who do not complete the study and provided using the above card at the end of the first study visit. While not a direct incentive, participants will be provided with three complete meals and snacks during each study visit that comply with a low plant diet (section I.4.).

H. INTERVENTION

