Each sachet will be dispensed to a member of the study team just prior to the participant's study visit and recorded by the Pharmacy staff including the date, participants ID number and dosage for accountability. Participants will receive two single administration doses of the *Centella asiatica* product equivalent to 2g and 4g of *Centella asiatica* water extract. The order in which they receive these doses will be random to prevent a tolerance effect. The doses selected are based on allometric scaling¹⁰⁴ from previous murine studies, which showed that 1.4 g/day of *Centella asiatica* water extract for a 70 kg human was equivalent to the 200 mg/kg/day estimated intake in mice. Participants will consume CAP in the presence of a member of the research team following baseline measurements, in order to ensure adherence to the study protocol. Following study completion, the remaining intervention and placebo sachets will be provided to [name] for destruction.

H.2. Administration

The study intervention will be administered in an outpatient setting. The research pharmacy will dispense one dose of CAP to a member of the study team, who will reconstitute the CAP powder in 8-12 ounces of warm water and provide it to the participant for oral consumption. One dose will be administered at each study visit in a random order.

H.3. Modification to study intervention

There will be no modifications to the study intervention during the study unless there are adverse events are noted and recommendations are made by the study's Independent Monitoring Committee (IMC).

Figure 4: Redacted

H.4. Criteria for intervention discontinuation and stopping guidelines

Participants will be advised during the informed consent process that they have the right to permanently discontinue the *Centella asiatica* product and/or withdraw from the study at any time without negative repercussions. Participants will also be counseled during the consent process that they may be withdrawn from the study at the discretion of the Principal Investigator or designees. A participant may discontinue and/or withdraw and/or be withdrawn from the study for the following reasons:

Administrative:

- 1) Withdrawal of participant consent
- 2) Request of site investigator or designees
- 3) Request of primary care physician
- 4) Non-compliance
- 5) Protocol deviation
- 6) Premature termination of the study

Study Title: A pharmacokinetic study of *Centella asiatica* in the elderly

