Power analysis and sample size estimation for the dose-dependent pharmacokinetics of *Centella asiatica* analytes were derived from the literature, specifically the plasma dose response analysis of the triterpene asiatic acid by Grimaldi et. al.⁴⁵ after single acute administration of 30 mg and 60 mg of a *Centella asiatica* triterpene fraction. In a repeated measures cohort of 12 males, they found significant differences ($p<0.05$) in asiatic acid's peak plasma concentration (C_{max}) (30 mg: $0.70 \mu\text{g/ml} \pm 0.38$; 60 mg: $1.36 \mu\text{g/ml} \pm 0.45$; $d=1.57$) and 24-hour total bioavailability (AUC_{0-24}) (30 mg: 4.16 ± 3.81 ; 60 mg: 9.39 ± 3.53 ; $d=1.42$) between the two doses. This paper was chosen as an analog for the current study since a proportionally equimolar dose response shift in the pharmacokinetic profile of asiatic acid can be expected of the proposed *Centella asiatica* product doses. Under that assumption, a significant within-group dose response at $\alpha=0.05$ with at least 80% power would be found for C_{max} with six participants and for AUC_{0-12} with seven participants. Even if the inclusion of additional compounds in the

Study Title: A pharmacokinetic study of *Centella asiatica* in the elderly

Principal Investigator: [name]

IRB#: 17697

Date: Feb 28 2024

Protocol v4.0

water extract reduces the dose effect anticipated in the current study, a significant difference in the pharmacokinetic outcomes would still be seen with eight participants. We therefore, propose a cohort of four men and four women, which will enable dose responses to be seen within each gender individually, and allow for evaluation of an attenuated response by pooling gender or provide protection against study dropout.

L.3. Data quality and management

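### Dose order is not stated to be randomised within sex: with four women and four men, 34 of 70 overall-balanced allocations leave order unbalanced in both sexes, which exposes the sex-specific dose effects to any period effect

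*Combined protocol and SAP*

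**What the plan says.** **Sex as a quota.** Section F.2.1: "Eight non-demented elderly volunteers (n=4 each female and male) 65-85 years of age will be screened and enrolled in the study".

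**Sex as something to be analysed.** Section C.1: "As part of this proposed project we will evaluate potential gender differences in bioavailability and pharmacokinetics". Section L.2 defends the four-plus-four cohort as one "which will enable dose responses to be seen within each gender individually". Section L.1 lists gender among the covariates of the regression model.

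**Allocation.** Section F.1: "This is a phase 1 pilot clinical study using a blinded randomized crossover design", followed by "Randomization will use an arm equivalence design to promote equal numbers of participants for each order schema". The term for the method is not defined, and no stratification factor or block size is given. Section H.1 adds: "The order in which they receive these doses will be random to prevent a tolerance effect". Section G: "Participants will be enrolled on a rolling basis until the desired number of participants is achieved", so nothing controls the sequence in which men and women reach the allocation list.

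**Analysis.** Section L.1 evaluates dose effects by paired t-tests and by least-squares regression on an open-ended set of confounders, of which age and gender are named. Period and sequence are not named.

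**The concern.** In a two-period crossover, each person's 4 g minus 2 g difference also contains the difference between visit 2 and visit 1, with a sign that depends on which dose came first. Equal numbers per order cancel this in the mean. If the numbers are equal over all eight people but unequal within a sex, it cancels in the pooled mean but not in the sex-specific means. Because overall balance forces the opposite imbalance in the other sex, the two errors add in the comparison of the sexes.

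A visit effect (familiarity with the visit or diet adherence, for example) could then look like a sex difference in dose response. The protocol already treats order as worth protecting against. That protection is not stated at the level where L.2 promises to read results.

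**Working it through.** **Inputs.** Four women and four men (F.2.1); two dose orders, aimed at equal numbers (F.1); two-sided 0.05, paired comparison (L.1); standardised effects 1.57 for Cmax and 1.42 for AUC (L.2).

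**1. The plan's own figures.** Exact paired-t power (noncentral t, n-1 df, two-sided 0.05), with the stated d taken as the standardised within-person difference:
- d = 1.57: 74.7% at n = 5 and 86.3% at n = 6, so the stated six is reproduced.
- d = 1.42: 79.2% at n = 6 and 87.6% at n = 7, so the stated seven is reproduced.
- At n = 4, one sex alone: 56.7% for Cmax and 49.3% for AUC.

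**2. Allocations.** With exactly four people per order, there are C(8,4) = 70 equally likely allocations. The number with k women in a given order is C(4,k) × C(4,4-k).

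| Split by order, one sex and the other | Allocations | Share |
|---|---|---|
| 2:2 and 2:2 | 6 × 6 = 36 | 51.4% |
| 3:1 and 1:3 (either way) | 2 × 4 × 4 = 32 | 45.7% |
| 4:0 and 0:4 (either way) | 2 × 1 × 1 = 2 | 2.9% |

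Unbalanced: 34/70 = 48.6%. Permuted blocks of 2, 4 or 8, averaged over all arrival orders of men and women, give the same share. If overall balance is not enforced, simple randomisation gives 2:2 in both sexes in only 36/256 = 14.1%.

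**3. Effect of a period difference.** Let P be visit 2 minus visit 1. A person's difference is δ + P if 2 g came first and δ - P if 4 g came first. With a and b people in the two orders, the sex-specific mean is shifted by P(a-b)/(a+b).
- 2:2: 0.
- 3:1 and 1:3: +P/2 and -P/2; sex contrast P.
- 4:0 and 0:4: +P and -P; sex contrast 2P.
- Pooled over all eight at 4:4: 0 in every case.

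The documents give no value for P. For illustration only, assume 0.10, 0.20 or 0.30 on the natural-log scale. The spurious sex ratio in dose effect would be exp(P) = 1.11, 1.22 or 1.35 at 3:1, and exp(2P) = 1.22, 1.49 or 1.82 at 4:0.

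**4. What adjustment recovers.** Let σ² be the variance of a within-person difference.
- Balanced 2:2: sex-specific effect σ²/4 = 0.250σ²; contrast 0.500σ².
- 3:1, one period term common to both sexes: the order code (±1) has within-sex sum of squares 4 - 4(0.5)² = 3, so 6 over both sexes, and Var(P̂) = σ²/6. Sex-specific effect: σ²(1/4 + 0.25/6) = 0.292σ², 17% more. Contrast: σ²(1/4 + 1/4 + 1/6) = 0.667σ², 33% more.
- 3:1, period fitted separately by sex: sex-specific effect (σ²/4)(1/3 + 1) = 0.333σ², 33% more; contrast 0.667σ², again 33% more.
- 4:0: order does not vary within a sex, so period cannot be separated from the sex contrast under either model.

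**The case against.** Several points on the other side stand.

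- **Silence is not a statement.** A reader might infer that the plan balances order only overall. No section says so. The allocation method is undefined, and the study design figure is not available to check. The supportable statement is that stratification by sex is not stated.
- **Sex is not an aim or endpoint.** A reader might take sex differences for a study aim. Neither Specific Aim mentions sex, nor do the primary goal and endpoints. It is a stated intention in the background and in the sample-size rationale.
- **The main comparison is safe.** The pooled within-person dose effect carries no period bias at 4:4.
- **A period effect may be small.** Visits are two to four weeks apart, enrolment is rolling, and fasting, the 48-hour diet and diaries limit drift. Averaged over the randomisation, the shift is zero; it is a shift conditional on the allocation drawn.
- **Adjustment works in most cases.** With a period term, the bias is absent or removed in 68 of 70 allocations. The open-ended covariate list in L.1 leaves room for one.
- **Precision is the larger limit.** From L.2, the SD of Cmax differences is (1.36 - 0.70)/1.57 = 0.42 µg/ml. The sex contrast then has standard error 0.42 × √(1/4 + 1/4) = 0.30 and a 95% half-width of 2.447 × 0.297 = 0.73 (6 df), wider than the whole expected dose effect of 0.66. An assumed 20% period effect on a mean of 1.03 is 0.21, under one standard error.

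These points limit the importance of the concern but do not remove it. That the sex-specific analysis is weak is no reason to leave in an avoidable source of confounding, and room for a period term is not a plan to fit one.

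**Conclusion.** The concern holds as an unstated protection for the sex-specific analyses, not as a flaw in the main dose comparison. If order is balanced 4:4 overall and not stratified by sex, the chance that both sexes are unbalanced is 48.6%; since F.1 only promotes equal numbers, that is the favourable case. The consequence depends wholly on a period effect whose size the documents do not give. A reader might infer that period adjustment cannot repair the problem. That is true only of the 2 allocations in 70 at 4:0; at 3:1 the price is the variance loss shown, not residual bias. The variance results assume equal variance of within-person differences in the two sexes, and the 17% figure also assumes one period effect common to both. Stratifying order by sex is a nearly free improvement. It would not make comparisons with four per sex more than exploratory.

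**What to change.** - **F.1:** state that dose order is randomised separately for women and for men, with two participants per order in each sex. At full enrolment the chance of within-sex imbalance falls from 48.6% to zero.
- **L.1:** include a period term in the dose-effect model, for example by regressing the within-person difference on sex and on order coded ±1. F.2.1 expects 10% dropout and allows for 25%, either of which can break a 2:2 split.
- **If allocation has already taken place:** report order by sex and fit the period term. If the list is already stratified by sex, a sentence in F.1 saying so settles the allocation point.
- **L.2:** describe the sex-specific analyses as exploratory.

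Cost: two short lists at the research pharmacy in place of one, and one residual degree of freedom for a common period term (7 to 6 in the pooled analysis of eight differences). The last place in a list of four can be predicted, but the study is blinded and both orders give the same two doses.

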Pharmacokinetics of *Centella asiatica* in the Elderly

NCT03929250

STUDY PROTOCOL INCLUDING STATISTICAL ANALYSIS PLAN

Document Version Date: February 28, 2024

Study Title: A pharmacokinetic study of *Centella asiatica* in the elderly

Principal Investigator: [name]

IRB#: 17697

Date: Feb 28 2024

Protocol v4.0

Title: A pharmacokinetic study of *Centella asiatica* in the elderly

A. OBJECTIVES

A.1. Purpose

The purpose of this pilot study is to measure the oral bioavailability and pharmacokinetics of known bioactive compounds from a standardized *Centella asiatica* water extract product (CAP) in cognitively healthy elders. Compound levels will be measured in human plasma and urine over 12 hours after acute oral administration of two doses of the botanical extract product. The dose giving maximum plasma levels (C_{max}) closest to those observed in our mouse studies, as well as the rate of clearance ($t_{1/2}$) of the known compounds, will be identified. These data will be used to inform decisions on the dosage and dosing frequency for future phase 1 and phase 2 clinical trials.

A.2. Primary goal

To determine the oral bioavailability and pharmacokinetics of known compounds from two single administrations of a *Centella asiatica* product in non-demented elders.

A.3. Endpoints

- The primary endpoints for this study are the maximum concentration (C_{max}), the area under the curve (AUC), and the time of maximum concentration (t_{max}) of known compounds from *Centella asiatica* (triterpenes and caffeoylquinic acids and their metabolites) in human plasma.
- A secondary endpoint is the half-life ($t_{1/2}$) of the known bioactive compounds and their metabolites to help determine dosage intervals.
- Additional secondary endpoints include temporal changes in ferric reducing ability of plasma (FRAP) as an indicator of antioxidant potential over time, tolerability and detection of acute adverse events through monitoring by participant interviews, biometrics, vital signs and questionnaires.

B. SPECIFIC AIMS

Aim 1: To assess the bioavailability and rate of clearance of *Centella asiatica* derived compounds in cognitively healthy elders through a pharmacokinetic study.

- **Hypothesis:** We hypothesize that the triterpene and caffeoylquinic acid components from *Centella asiatica* will be bioavailable, and a dose giving similar plasma levels to those associated with cognitive effects in mice can be achieved.

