Each analyte of interest from *Centella asiatica* will be identified by its retention time and characteristic mass spectral fragmentation pattern using selected reaction monitoring (MS/MS). The peak area ratio to the appropriate internal standard will be identified and evaluated against the standard calibration curve of each analyte. Each analyte's concentration will be used to generate a concentration-time curve for pharmacokinetic profiling. Pharmacokinetic profiling will use non-compartmental analysis to calculate common pharmacokinetic parameters such as peak concentration (C_{max}), the time at peak concentration (t_{max}) and the total 12-hour bioavailability represented by the total area under the curve (AUC_{0-12}). These will be compared to our mouse data in order to assess appropriateness of dosing level. Other calculable non-compartmental analysis metrics will also be determined, such as the elimination half-life ($t_{1/2}$) calculated from the profile tails and the mean residency time of the compounds in plasma. Descriptive assessment will be done at each of the doses to give basic pharmacokinetic summarization of the various *Centella asiatica* compounds and total antioxidant compounds measured by ferric reducing ability of plasma. Dose dependence of the study outcomes will be determined by evaluation of the within-subject differences in study outcomes between the different doses. For all continuous variables, dose effects will be evaluated both naively using paired t-tests and with ordinary least-squares regression with correction for commonly cited confounders including but not limited to baseline age and gender. Assumptions of normality will be confirmed using outcome density distributions alongside utility from formal tests, such as the Anderson-Shapiro. In instances of normality violation, statistical transformation such as natural logs and square roots will be considered, as will non-parametric equivalent tests such as the paired Wilcoxon rank-sum test. Standard diagnostics will be very conservative given the limited number of available participants but the effect of removing clearly obvious outliers will be evaluated. Although all *Centella asiatica* compounds of interest and pharmacokinetic parameters are defined *a priori*, multiple comparison correction to p-values will be applied as necessary, with final two-tail significance defined at $p<0.05$.

L.2. Sample size

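### The plan claims more power than L.2's own sizing supports: slightly for AUC at six completers (F.2.1), and clearly for four participants per gender (L.2)

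*Combined protocol and SAP*

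**What the plan says.** F.2.1 plans eight participants, four of each gender, and expects 10% dropout. It then says: "We are still powered to see changes from baseline and differences between doses with a 25% drop out rate resulting in 6 subjects". It names no endpoint and no power level.

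L.2 takes its effects from a published study of asiatic acid in 12 men after 30 mg and 60 mg of a triterpene fraction: d = 1.57 for Cmax and d = 1.42 for AUC0-24. At alpha 0.05 it finds at least 80% power for Cmax "with six participants and for AUC_{0-12} with seven participants". It adds that, even with a weaker effect, "a significant difference in the pharmacokinetic outcomes would still be seen with eight participants". It justifies the split of four men and four women as one "which will enable dose responses to be seen within each gender individually", with pooling of the genders as cover for a weaker response or for dropout.

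A.3 says "The primary endpoints for this study are the maximum concentration", and lists AUC and tmax beside it. L.1 specifies paired t-tests with two-sided significance at 0.05, and says that "multiple comparison correction to p-values will be applied as necessary".

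**The concern.** If seven are needed for AUC0-12, then six cannot meet the same standard for it, and F.2.1's unqualified assurance conflicts with L.2 for one of the primary endpoints. If six or seven are needed for the pooled comparison, then four cannot meet that standard within one gender.

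What is at stake is how the results are read. A team relying on F.2.1 would treat a non-significant AUC difference in six completers as adequately powered. A team relying on L.2 would treat a non-significant result in one gender as evidence that it lacks a dose response, when at L.2's own effects such a result is about as likely as not. The pharmacokinetic estimates themselves, and the choice of the dose whose Cmax lies closest to the mouse data (A.1), do not depend on power.

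**Working it through.** **Inputs.** From L.2: d = 1.57 (Cmax) and 1.42 (AUC), alpha 0.05, target 80%. From L.1: paired t-test, two-sided. From F.2.1: n = 8, so 8 × 0.90 = 7.2 completers at 10% dropout and 8 × 0.75 = 6 at 25%. Per gender: n = 4.

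**Formula.** Power = P(|T| > t(0.975; n−1)), where T is noncentral t with n−1 degrees of freedom and noncentrality d√n. L.2's d is taken as the mean paired difference divided by its SD.

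| n | critical t | noncentrality Cmax / AUC | power Cmax | power AUC |
|---|---|---|---|---|
| 4 | 3.182 | 3.14 / 2.84 | 56.7% | 49.3% |
| 5 | 2.776 | 3.51 / 3.18 | 74.7% | 66.6% |
| 6 | 2.571 | 3.85 / 3.48 | 86.3% | 79.2% |
| 7 | 2.447 | 4.15 / 3.76 | 93.0% | 87.6% |
| 8 | 2.365 | 4.44 / 4.02 | 96.6% | 92.9% |

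**The plan's figures reproduce.** The smallest n reaching 80% is 6 for Cmax and 7 for AUC, as L.2 states. A simulation of 400,000 runs at n = 6 gave 86.4% and 79.2%. Other readings do not return 6 and 7: a one-sided 0.05 test already gives 82.9% for AUC at five, and a two-sample z calculation gives 7 and 8 per arm. L.2's sizes are therefore those of single asiatic acid tests at an uncorrected two-sided 0.05.

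**F.2.1's claim.** At six, Cmax passes (86.3%) and AUC misses 80% by 0.8 points. At seven, both pass.

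**L.2's gender claim.** At four, Cmax misses 80% by 23.3 points and AUC by 30.7.

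**Dependence on correlation.** From L.2's means and SDs, d = (m2 − m1) / √(s1² + s2² − 2·r·s1·s2). At r = 0.5:

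- Cmax: (1.36 − 0.70) / √(0.38² + 0.45² − 0.38 × 0.45) = 0.66 / 0.419 = 1.574.
- AUC: (9.39 − 4.16) / √(3.81² + 3.53² − 3.81 × 3.53) = 5.23 / 3.678 = 1.422.

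So L.2's d values correspond to r near 0.5, which the documents do not give. Treating r as an assumption:

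| r | d Cmax / AUC | power at n = 6 | power at n = 4 |
|---|---|---|---|
| 0.3 | 1.335 / 1.203 | 74.4% / 65.7% | 45.0% / 38.5% |
| 0.5 | 1.574 / 1.422 | 86.5% / 79.3% | 56.9% / 49.4% |
| 0.7 | 2.013 / 1.832 | 97.2% / 94.3% | 76.0% / 68.8% |

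**Dependence on the AUC window.** L.2 applies an AUC0-24 effect to AUC0-12. If the AUC0-12 effect were anywhere from 1.2 to 1.57, AUC power at six would run from 65.5% to 86.3%.

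**Caution on multiplicity.** As an illustration only, Bonferroni over an assumed two tests (two-sided 0.025) gives 73.0% / 63.8% at six and 91.2% / 84.6% at eight.

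**The case against.** On F.2.1, the discrepancy is under one percentage point, F.2.1 quotes no 80% standard, and the plan's expected dropout leaves enough participants for both endpoints. L.2 also names dropout as one of the uses of its reserve. All of this stands. F.2.1's sentence is a statement about a contingency and is wrong only for AUC, by little. It still conflicts with L.2 as text.

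On gender, one could say that L.2 promises only that responses can be looked at within each gender, not tested. The wording does not favour this. The sentence is drawn as a conclusion from the power figures, the sentence before it uses the same verb for a significant difference, and pooling is offered separately for a weaker response.

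A reader might go further and infer that six completers have only 73% and 64% power because of multiplicity. The documents do not support that. L.1 leaves correction open, names neither Bonferroni nor a family of two, and says that the compounds and parameters are set in advance; L.2 sizes at 0.05. If the dose p-values are left uncorrected and reported as descriptive, which would suit a pilot, that loss does not arise.

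Nor can one say that AUC at six falls below 80% whatever is assumed: at a correlation of 0.7 it is 94%.

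**Conclusion.** The concern holds in a limited form. L.2's six and seven are right at the alpha it states. F.2.1 overstates what six completers give for AUC0-12 (79% against 80%), and only at 25% dropout. L.2's within-gender claim is the larger error: 57% for Cmax and 49% for AUC, and still at most 76% and 69% at a correlation of 0.7, so it misses 80% across the whole assumed range of 0.3 to 0.7.

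The point estimates rest on four assumptions taken from L.2: d values read as paired effects, the AUC0-24 effect standing in for AUC0-12, effects from men applied to both genders, and one uncorrected asiatic acid test. Any correction under L.1 would lower the figures, by an amount the plan does not determine.

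**What to change.** **F.2.1:** state that, at L.2's assumptions, six completers give 86% power for Cmax and 79% for AUC0-12, and that AUC0-12 needs seven completers for 80%.

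**L.2:** withdraw the within-gender claim, or restate it as 57% for Cmax and 49% for AUC at four per gender and report the by-gender results as descriptive. State that 80% refers to a single asiatic acid test at an uncorrected two-sided 0.05, that d is a paired effect with an implied correlation near 0.5, and that the AUC effect is the 24-hour one.

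Beside these figures, note that any correction applied under L.1 would reduce them.

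**Cost:** the stated power becomes less favourable and the gender split loses its power-based justification. No participants, visits or samples are added, and the planned tests do not change.
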